**Overall Responses Derived from Changes in Index, Non-Index, and New Lesions**

Measurable Response	Non-Measurable Response		Overall Response Using Modified irRC
Index and New, Measurable Lesions	Non-Index Lesions	New, Non-Measurable Lesions	
Decrease 100%	Absent	Absent	irCR 
Decrease 100%	Stable	Any	irPR 
Decrease 100%	Unequivocal progression	Any	irPR 
Decrease $\geq 30\%$	Absent / Stable	Any	irPR 
Decrease $\geq 30\%$	Unequivocal progression	Any	irPR 
Decrease $< 30\%$ to increase $< 20\%$	Absent / Stable	Any	irSD
Decrease $< 30\%$ to increase $< 20\%$	Unequivocal progression	Any	irSD
Increase $\geq 20\%$	Any	Any	irPD

 Decreases assessed relative to baseline

 Assuming that the response (irCR and irPR) and progression (irPD) are confirmed by a second, consecutive assessment at least 4 weeks apart (normally it should be done 6 weeks apart).

Post Ablation changes observed on radiographic studies that are larger in size than preablation masses will not be considered tumor progression if no enhancement within the lesion that suggests tumor growth.

**8.0 PATIENT REGISTRATION**

All patients will be registered through the Brown University Oncology Research Group Central Office. Eligibility Checklist with supporting documentation, On Study Form and the signed Patient Consent Form must be faxed to the BrUOG Central Office, [contact], at the time of registration and prior to patient treatment.

Details of patient's study participation should be documented in clinic/file notes. The Brown University Oncology Research Group will provide case report forms, for the recording and collection of data. In the event of corrections, each correction will be initialed and dated by the person making the correction. The investigator will sign the case reports to indicate that, to his/her knowledge, they are complete and accurate. Case report forms, flow sheets, off-study forms and follow-up forms should be mailed / faxed to:

## **9.0 PHARMACEUTICAL INFORMATION OF NIVOLUMAB**

Only commercially available nivolumab (OPDIVO) will be utilized.

Nivolumab will be stored and administered according to the package insert and institutional standard of care.

### **Preparation and Administration**

Visually inspect drug product solution for particulate matter and discoloration prior to administration. OPDIVO is a clear to opalescent, colorless to pale-yellow solution. Discard the vial if the solution is cloudy, is discolored, or contains extraneous particulate matter other than a few translucent-to-white, proteinaceous particles. Do not shake the vial.

#### ***Preparation***

- Withdraw the required volume of OPDIVO and transfer into an intravenous container.
- Dilute OPDIVO with either 0.9% Sodium Chloride Injection, USP or 5% Dextrose Injection, USP, to prepare an infusion with a final concentration ranging from 1 mg/mL to 10 mg/mL.
- Mix diluted solution by gentle inversion. Do not shake.
- Discard partially used vials or empty vials of OPDIVO.

#### ***Storage of Infusion***

The product does not contain a preservative.

After preparation, store the OPDIVO infusion either:

- at room temperature for no more than 4 hours from the time of preparation.

FDA exemption 6/30/15, 6/30/15, 8/17/15 (for LOCR initial), Amendment #1 10/5/15 v 2 HS approval, Amendment # 2 11/9/15, 17  
Amendment #3 3/4/16, Amendment # 4 4/7/16, Amendment # 5 6/1/16 V2, Amendment # 6 7/7/16, Amendment # 7 11/16/16,  
Amendment # 8 2/22/17, Amendment #9 5/22/17

This includes room temperature storage of the infusion in the IV container and time for administration of the infusion or

- under refrigeration at 2°C to 8°C (36°F-46°F) for no more than 24 hours from the time of infusion preparation.

Do not freeze.

### ***Administration***

Administer the infusion over approximately 60 minutes through an intravenous line containing a sterile, non-pyrogenic, low protein binding in-line filter (pore size of 0.2 micrometer to 1.2 micrometer).

Do not co-administer other drugs through the same intravenous line.

Flush the intravenous line at end of infusion.

### ***DOSAGE FORMS AND STRENGTHS***

Injection: 40 mg/4 mL (10 mg/mL) and 100 mg/10 mL (10 mg/mL) solution in a single-use vial.

Dosage: Subjects will be treated with 3mg/kg up to a maximum dose of 240mg of nivolumab as an approximate 60 minute IV infusion every 2 weeks.

Immuno-oncology (I-O) agents are associated with adverse events that can differ in severity and duration than adverse events caused by other therapeutic classes. Nivolumab is considered an immuno-oncology agent in this protocol. Early recognition and management of adverse events associated with immuno-oncology agents may mitigate severe toxicity. Immune Toxicities may include:

- Pulmonary (pneumonitis)
- Gastrointestinal (colitis with diarrhea)
- Endocrinopathies (including inflammation of the thyroid, adrenal and pituitary)
- Hepatic (hepatitis)
- Renal (nephritis)
- Skin (rash)
- Neurological (neuritis)

## **10.0 AGENT ACCOUNTABILITY**

Commercial nivolumab will be used in this trial, therefore there will be no drug accountability.

## **11.0 ADVERSE DRUG REACTION (ADR) REPORTING**

***BrUOG considers the SAE reporting period to begin when the subject signs the study specific informed consent.***

This study will utilize the descriptions and grading scales found in the NCI Common Terminology Criteria for Adverse Events (CTCAE) version 4 for grading all adverse events. All appropriate treatment areas should have access to a copy of the CTCAE version 4. A copy of the CTCAE version 4 can be downloaded from the CTEP web site (<http://ctep.cancer.gov>).

An Adverse Event (AE) is defined as any untoward medical occurrence in a patient or clinical investigation subject administered a pharmaceutical product and that does not necessarily have to

FDA exemption 6/30/15, 6/30/15, 8/17/15 (for LOCR initial), Amendment #1 10/5/15 v 2 HS approval, Amendment # 2 11/9/15, 18  
Amendment #3 3/4/16, Amendment # 4 4/7/16, Amendment # 5 6/1/16 V2, Amendment # 6 7/7/16, Amendment # 7 11/16/16,  
Amendment # 8 2/22/17, Amendment #9 5/22/17

have a causal relationship with this treatment. An AE can therefore be any unfavorable and unintended sign (including an abnormal laboratory finding), symptom, or disease temporally associated with the use of Abraxane whether or not considered related to Abraxane. This includes any newly occurring event or previous condition that has increased in severity or frequency since the administration of drug.

During clinical trials, adverse events can be spontaneously reported or elicited during open-ended questioning, examination, or evaluation of a subject. (In order to prevent reporting bias, subjects should not be questioned regarding the specific occurrence of one or more adverse events.)

Adverse events (AEs) will be recorded in the case report form for the duration of the trial, regardless of whether or not the event(s) are considered related to trial medication. All AEs considered related to trial medication will be followed until resolution even if this occurs post-trial.

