## **5.2 The following must be confirmed prior to dosing a patient with Nivolumab:**

- 1) Patients experiencing treatment related (drug) grade 4 or treatment related (drug) clinically significant grade 3 toxicities must have toxicity resolved to grade 2 or less prior to resuming nivolumab.

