## **5.3 Hold treatment until recovery to grade 1 or resolution for:**

- 1) If AST or ALT >3 to 5 times ULN (grade 2) or total bilirubin >1.5 to 3 times ULN (grade 2): **Withhold treatment**; may resume therapy upon recovery to grade 0 or 1 toxicity (AST/ALT grade 1 is >ULN-3xULN, Total bilirubin grade 1 is >ULN-1.5xULN).

\*\*for possibly, probably or definitely related to nivolumab see section 5.3, 2.I below

\*\*AST or ALT >5 times ULN (grade 3) or total bilirubin >3 times ULN (grade 3) or severe/life-threatening immune-mediated hepatitis: **Permanently discontinue**. \*\*see section 5.3 (this section), 2\*\* below

- 2) Immune-mediated hepatitis:

- I. Grade 2 or higher transaminase elevations that are possibly, probably or definitely related to nivolumab (with or without total bilirubin elevations): Withhold treatment and initiate high-dose systemic corticosteroids (prednisone 1 to 2 mg/kg daily or equivalent)

\*\* Severe (grade 3) or life-threatening (grade 4) transaminase elevations: Permanently discontinue treatment and initiate high-dose systemic corticosteroids (prednisone 1 to 2 mg/kg daily or equivalent)

- 3) **Colitis:**

- I.** Grade 2 (duration >5 days): Also administer systemic corticosteroids (prednisone 0.5 to 1 mg/kg daily or equivalent) followed by a corticosteroid taper; may increase to prednisone 1 to 2 mg/kg daily (or equivalent) if colitis worsens or does not improve despite corticosteroid use
- II.** Grade 3: Also administer systemic corticosteroids (prednisone 1 to 2 mg/kg daily or equivalent) followed by a corticosteroid taper

- 4) **Pneumonitis:** Pneumonitis (grade 2); also administer high-dose systemic corticosteroids (prednisone 1 to 2 mg/kg daily or equivalent) followed by a corticosteroid taper

- 5) **Other immune-mediated toxicities:** Other immune-mediated toxicities; also administer high-dose systemic corticosteroids followed by a corticosteroid taper (over 1 month)

- 6) **Creatinine** >1.5 to 6 times ULN (grade 2 or 3) or >1.5 times baseline (grade 1): Withhold treatment; administer prednisone 0.5 to 1 mg/kg daily (or equivalent) followed by a corticosteroid taper; may resume therapy upon recovery to grade 0 or 1 toxicity. If toxicity worsens or does not improve, permanently discontinue and increase corticosteroid dose to prednisone 1 to 2 mg/kg daily (or equivalent).

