Q- Physical and visit with treating MD is not required prior to each cycle dosing but may be done. It is required that the physical and visit with MD occur every other cycle however (i.e. cycle 1 (if PE not within time frames allowed from screening visit), 3, 5, 7 etc and at end of study treatment and 30 days.) All other pre-dosing assessments are required prior to each cycle.

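### The advice in Section 11.0 against asking about specific adverse events sits badly with the plan's reliance on early recognition of immune toxicity, and weakens first detection of symptom-based events

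*Protocol*

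**What the plan says.** Section 11.0 of the Protocol allows several routes to an adverse event: "adverse events can be spontaneously reported or elicited during open-ended questioning, examination, or evaluation of a subject". The parenthetical that follows narrows this. To avoid reporting bias, "subjects should not be questioned regarding the specific occurrence of one or more adverse events".

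Section 9.0 (Dosage Forms and Strengths) takes a different line for this drug class: "Early recognition and management of adverse events associated with immuno-oncology agents may mitigate severe toxicity". It then lists seven classes of immune toxicity: pulmonary, gastrointestinal, endocrine, hepatic, renal, skin and neurological. One entry reads "Gastrointestinal (colitis with diarrhea").

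Sections 5.3 and 5.4 attach holding or permanent discontinuation to the grade of these events. Pneumonitis is held at grade 2 and discontinued at grade 3 or 4. Colitis is held at grade 2 beyond a stated duration and at grade 3, and discontinued at grade 4 or on recurrence.

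The Section 6.0 calendar puts a toxicity assessment before every cycle, together with weight, vital signs, performance status and laboratory tests. Footnote Q relaxes one element: "Physical and visit with treating MD is not required prior to each cycle dosing but may be done". The examination and physician visit are required every other cycle (1, 3, 5, 7 and so on). The same footnote keeps all other pre-dose assessments mandatory at each cycle.

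**The concern.** A coordinator who follows Section 11.0 literally would not ask, before a dose, whether the patient has had diarrhoea, cough, breathlessness, rash or numbness. Those are the complaints through which several of the Section 9.0 toxicities would first show themselves. The calendar gives no symptom list, and no text says that the clinical toxicity assessment falls outside the Section 11.0 advice.

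Two things are at stake. A symptom that the patient does not mention could go unrecognised before the next infusion. And the cumulative toxicity summaries that the DSMB uses under Section 16.0 to judge whether the trial should continue could understate symptom-based events, for a drug-plus-ablation combination.

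The stated reason for the advice has little force here. Section 17.1 describes a non-randomized phase II trial, so there is no concurrent comparison of toxicity between groups to protect from leading questions.

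**Working it through.** This is mainly a comparison of texts. The steps are as follows.

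1. **What Section 11.0 restricts.** It concerns prompting about whether a specific event has occurred. It is worded as advice (should not). Open-ended questions, examination and evaluation remain available.

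2. **Which toxicities have another scheduled marker.** Per-cycle chemistry includes AST, ALT, bilirubin and creatinine, so the hepatic and renal classes have direct laboratory markers. TSH is scheduled pre-study only, and no other hormone test is listed. That leaves 7 - 2 = 5 classes (pulmonary, gastrointestinal, endocrine, skin, neurological) that depend mainly on symptoms or examination.

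3. **When the restriction bites.** On cycles 1, 3, 5, 7 and so on, an examination and physician visit supplement the questions. On the cycles between, the scheduled inputs are the toxicity assessment, vital signs, weight, performance status, concomitant medications and laboratory tests. Symptom information then rests mainly on what the patient volunteers or says in answer to an open question. Cycle 2 is one of these cycles, and it is the first dose after the initial ablation if that takes place in cycle 1 as Section 4.2 plans.

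4. **Which rules depend on first detection.** The hold and stop rules for pneumonitis, colitis and other immune toxicities (Sections 5.3 and 5.4) act only once an event has been recognised and graded. Section 11.3 requires duration and intensity to be recorded for each episode, which again presupposes that the episode has surfaced.

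5. **Illustration of under-counting.** The documents give no capture rate for open-ended or directed questions, so this shows a range and is not an estimate. Let *t* be the true per-patient incidence, *c* the fraction of affected patients recorded by any route, and *n* the number of patients. Then P(no case recorded) = (1 - *t* × *c*)^*n*. The sample sizes 18 and 33 come from Section 17.1. The 10% incidence is assumed. The 3% is the pneumonitis figure in Section 2.0, which refers to the total population of an earlier nivolumab trial.

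| *t* | *n* | *c* = 1.0 | *c* = 0.8 | *c* = 0.5 |
|---|---|---|---|---|
| 10% | 33 | 0.90^33 = 3% | 0.92^33 = 6% | 0.95^33 = 18% |
| 10% | 18 | 0.90^18 = 15% | 0.92^18 = 22% | 0.95^18 = 40% |
| 3% | 33 | 0.97^33 = 37% | 0.976^33 = 45% | 0.985^33 = 61% |
| 3% | 18 | 0.97^18 = 58% | 0.976^18 = 65% | 0.985^18 = 76% |

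   At 10% incidence in 33 patients, expected recorded cases are 33 × 0.10 × *c* = 3.3, 2.6 and 1.7.

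6. **Effect on the primary analysis.** With 18 patients in stage 1, continuation at 5 or more responses and rejection at 11 or more of 33, P(reject) is the sum over *x* = 5 to 18 of P(X1 = *x*) × P(X2 ≥ 11 - *x*), where X1 ~ Bin(18, *p*) and X2 ~ Bin(15, *p*). This gives 0.0458 at *p* = 0.20 and 0.801 at *p* = 0.40, in line with the stated 0.05 bound and 80% power. Adverse event elicitation does not enter the calculation.

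**The case against.** The strongest reply is that the plan already looks actively for toxicity. An open question at a mandatory pre-dose assessment is elicitation, not passive waiting. The concomitant medication log, which covers agents given for toxicity, may reveal self-treatment. Examination at least every other cycle, the end-of-treatment and 30-day reviews and SAE reporting give further chances to find an event. Non-leading questioning is a stated choice with a stated reason. Safety is neither a primary nor a secondary objective, and Section 17 sets no toxicity boundary. Most of this stands, and it limits the point to weakened detection.

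Three stronger readings are tempting, and the documents support none of them.

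- **That a symptom the patient does not volunteer has no scheduled route to detection on alternate cycles.** The calendar and footnote Q require a toxicity assessment before every cycle. Only the examination and physician visit may be skipped.
- **That the pre-dose rules cannot be applied without forbidden questions.** Section 5.2 opens with "The following must be confirmed prior to dosing a patient with Nivolumab" and goes on to patients who already have a qualifying toxicity, who "must have toxicity resolved to grade 2 or less prior to resuming nivolumab". The colitis entry in Section 5.3, "Grade 2 (duration >5 days"), likewise concerns an event already identified. Section 11.0 discourages prompting about occurrence. It does not bar asking about the grade, duration or resolution of a known event, and Section 11.3 requires duration and intensity to be recorded.
- **That reported toxicity is biased low as a matter of fact.** The direction is plausible for symptom-based events, but its presence and size rest on capture fractions that the documents do not give. Even with full capture, a 3% event would be absent from 33 patients 37% of the time. The missing on-study TSH adds nothing to the re-dosing worry, because Section 5.6 recommends no dosage modification for thyroid disorders.

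What the reply does not answer is that, read literally, Section 11.0 applies to the pre-dose assessment as well. Clinicians who ask anyway would depart from the text, and capture would then vary by site. The adverse event definition just above the parenthetical refers to Abraxane, which is not a study drug. This suggests, without proving it, that the section was carried over from another protocol.

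**Conclusion.** The point holds in limited form. Section 11.0 is in tension with Section 9.0 and with the grade-based hold and stop rules in Sections 5.3 and 5.4. The effect is to weaken first detection of symptom-based immune toxicity, chiefly on alternate cycles. Toxicity summaries may under-count such events.

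The size is unknown. In the illustration for 33 patients, moving from full to 80% or 50% capture raises the chance of recording no case by about 3 to 15 percentage points at 10% incidence, and by about 8 to 24 points at 3%. Those figures depend entirely on the assumed incidence and capture, where capture means recording by any route over the whole of follow-up. The response endpoint, type I error and power are untouched. This is a cheap improvement to the safety data, not a threat to the primary conclusion.

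**What to change.** Reconcile Section 11.0 with Sections 5.3, 5.4, 6.0 (including footnote Q) and 9.0. Either delete the parenthetical, or state that it does not limit the toxicity assessment in the calendar.

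Then add one sentence on method: at each scheduled toxicity assessment, staff ask an open question first, then ask about symptoms of the immune toxicities listed in Section 9.0, and record each event as volunteered or elicited. The flag keeps a volunteered-only rate available for anyone comparing with historical series collected by open questioning.

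The cost is about one sentence of protocol text, one CRF field and a few minutes at visits that already take place. The downside is that more grade 1-2 events will be recorded. No dose, hold or stopping rule changes.

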### **11.1 Definitions**

**An adverse event** is any new, undesirable medical experience or change of an existing condition that occurs during or after treatment, whether or not considered product-related.

#### **Serious adverse event (SAE)**

An adverse event occurring at any dose that results in any of the following outcomes (CFR 312.32):

- death
- a life-threatening adverse drug experience
- inpatient hospitalization or prolongation of existing hospitalization excluding those for study drug administration, transfusional support, disease staging/re-staging procedures, concomitant radiotherapy, thoracentesis / paracentesis, or placement of an indwelling catheter, unless associated with other serious events.
- persistent or significant disability or incapacity,
- congenital anomaly / birth defect.

The definition of serious adverse event (experience) also includes *important medical event*. Medical and scientific judgment should be exercised in deciding whether expedited reporting is appropriate in other situations, such as important medical events that may not be immediately life-threatening or result in death or hospitalization but may jeopardize the patient or may require intervention to prevent one of the other outcomes listed in the definition above. These should also usually be considered serious. Examples of such events are intensive treatment in an emergency room or at home for allergic bronchospasm; blood dyscrasias or convulsions that do not result in hospitalization; or development of drug dependency or drug abuse. A new diagnosis of cancer during the course of treatment should be considered an important medical event.

The definition of “related” being that there is a reasonable possibility that the drug caused the adverse experience.

#### **Unexpected adverse event**

An adverse event that is not mentioned in the Investigator's Brochure or package insert or the specificity or severity of which is not consistent with the investigator's brochure or package insert.

## **Life-threatening**

Any adverse drug experience that places the patient or subject, in the view of the investigator, at immediate risk of death from the reaction as it occurred. It does not include a reaction that, had it occurred in a more severe form, might have caused death.

## **11.2 Monitoring of Adverse Events and Period of Observation**

Adverse events, both serious and non-serious, and deaths that occur during the patient's study participation will be recorded in the source documents. All SAEs should be monitored until they are resolved or are clearly determined to be due to a patient's stable or chronic condition or intercurrent illness(es).

## **11.3 BRUOG ADVERSE EVENT REPORTING REQUIREMENTS**

Investigators are required by Federal Regulation to report adverse drug reactions. Question regarding drugs as used in this study should be directed to the Brown University Oncology Research Group (BrUOG) Central Office, [contact] [contact], which will in turn notify the Principal Investigator.

Intensity for each adverse event will be scored using CTCAE Version 4. A copy of the CTCAE Version 4 can be downloaded from the CTEP homepage (<http://ctep.info.nih.gov>). All appropriate treatment areas have access to a copy of the CTCAE Version 4. All adverse clinical experiences, whether observed by the investigator or reported by the patient, must be recorded, with details about the duration and intensity of each episode, the action taken with respect to the test drug, and the patient's outcome. The investigator must evaluate each adverse experience for its relationship to the test drug and for its seriousness.

AEs and SAEs will be captured and reported from when the patient signs consent to 4 weeks post last dose of drug or until the subject withdraws consent from study participation (declines participation) or at the time patient becomes a screen failure, whichever occurs first.

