D- For patients who are removed from protocol treatment due to toxicity, without progression, Follow-up until disease progression will include CT, disease free and overall survival every 3 months (a month window is allotted for scheduling). CT scans may be done outside of the 3 month window as per MD discretion; however it is suggested that CT scans be done q 3 months. For patients who come off study for progression, overall survival is to be reported every 3 months (a month window is provided). Follow-up will be for 5 years.

E post-menopausal women (surgical menopause or lack of menses  $\geq 12$  months) do not need to have a pregnancy test, document status. If HCG is not drawn, sites are asked to document menopausal status on lab form.

F It is appropriate to use labs from screening for cycle 1 day 1, if labs are within 14 days (pregnancy must be within 7 days as noted above for applicable patients). A physical exam within 7 days prior to cycle 1 day 1 may be utilized. PS, weight, vitals, conmeds, and AE assessment can be used from screening for cycle 1 if assessments are within 14 days of treatment. Labs and physical exam for all subsequent cycles can be within 3 days prior to day 1 of treatment. Another day is provided for holidays.

G Physician note required to be sent. For ablation time points, sites are to submit consult notes from appointment pre-ablation and if consult occurs post ablation that not is also to be sent.

H Adverse event evaluation, inclusive of SAE evaluation, will be done 30 days post last dose of drug (+1 week window). SAEs occurring outside this 30 day window must be reported if the event is considered to be possibly related to the drug, even if patient begins a new treatment. If a patient begins a new treatment, AE evaluation will be stopped unless the patient experiences an event that is thought to be possibly related to the study treatment. It is required to inform BrUOG of patient beginning a new treatment.

I Physical to be done in coordination with 30 day toxicity assessment (+ 1 week allowed). Physical post 30 day assessments not required per study

JCT scans (or disease assessment by MRI or PET) to be completed approximately every 12 weeks (approximately every 6 cycles). For patients staying on study post initial PD – see section 7.3- next scan to confirm PD to be done in 1 month time period if patient remains on study.

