### **Expedited Reporting by Investigator to BrUOG**

Serious adverse events (SAE) are defined above. All events must be reported, by FAX or email to the Brown University Oncology Research Group. The initial report must be as complete as possible, including an assessment of the causal relationship between the event and the investigational product(s), if available. Information not available at the time of the initial report (e.g., an end date for the adverse event or laboratory values received after the report) must be documented on a follow-up report. A final report to document discharge is required.

This includes serious, related, labeled (expected) and serious, related, unlabeled (unexpected) adverse experiences. All deaths during treatment or within 30 days following completion of active protocol therapy (drug or ablation) must be reported within 5 business days of when the investigator is made aware of the event or as soon as the investigator is made aware of the event. Deaths that are thought to be related to drug are to be reported to BrUOG in 24 hours/1 business day of being made aware of the event. SAEs occurring within 30 days following completion of active protocol therapy (drug or ablation) will be captured even if patient begins a new treatment. AE evaluation will stop once patient begins a new treatment.

All adverse events and special reporting situations, whether serious or non-serious, related or unrelated, will be reported from the time a signed and dated ICF is obtained until 30 days after the last dose of nivolumab or ablation (whichever is last), or until the subject withdraws consent from study participation (declines participation) or at the time patient becomes a screen failure, whichever occurs first.

Serious adverse events occurring more than 4 weeks after study discontinuation need only be reported if a relationship to the study drug (or therapy/ablation) is suspected.

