#### **11.5 Types of Report:**

**Telephone report:** For SAE's contact BrUOG Central Office at [contact] within 24 hours upon learning of the event for notification and prior to submitting the SAE report.

**Written report:** Send the copy of the Medwatch 3500A within 5 business days of being made aware of the event to the BrUOG Central Office by email, scan or Fax:

Brown University Oncology Research Group

[contact], [contact]

Email: [[name]\\[contact]](mailto:[contact]), [[name]\\[contact]](mailto:[contact])

All deaths during treatment or within 30 days following completion of active protocol therapy (last dose of drug or ablation) must be reported within 5 business days of being made aware of the event or as soon as the investigator is made aware of the event. If the death is thought to be related to the study drug or ablation, deaths must be reported to BrUOG within 24 hours/1 business day of the investigator being made aware of the event. For pregnancies please refer to prior section.

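### The protocol gives conflicting windows for adverse-event capture, and only one of them counts from ablation, so events after an ablation given on or after the last nivolumab dose may be captured unevenly

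*Protocol*

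**What the plan says.** Several parts of the protocol set or imply the end of adverse-event (AE) and serious adverse-event (SAE) capture.

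- **Section 11.3:** "AEs and SAEs will be captured and reported from when the patient signs consent to 4 weeks post last dose of drug". Ablation does not appear in this window. The same section asks for causality to be judged against the test drug only.
- **Section 11.3.2, Expedited Reporting by Investigator to BrUOG:** all events, serious or not and related or not, are reported "until 30 days after the last dose of nivolumab or ablation (whichever is last". For SAEs it adds that "SAEs occurring within 30 days following completion of active protocol therapy (drug or ablation) will be captured even if patient begins a new treatment". Beyond 4 weeks after study discontinuation, SAEs "need only be reported if a relationship to the study drug (or therapy/ablation) is suspected".
- **Section 6.0, footnote H:** "Adverse event evaluation, inclusive of SAE evaluation, will be done 30 days post last dose of drug (+1 week window". Its rule for later SAEs names only the drug. The calendar column is also headed by days since the last drug dose.
- **Section 13.0:** a further AE evaluation at about 30 days after the last study drug.

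The rule for prompt reporting of related deaths varies in the same way. Section 11.5 reads "If the death is thought to be related to the study drug or ablation, deaths must be reported to BrUOG within 24 hours/1 business day", and Section 11.3.2 opens with an equivalent sentence. The Expedited Reporting text says only "Deaths that are thought to be related to drug are to be reported to BrUOG in 24 hours/1 business day".

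The AE definition in Section 11.0 refers to events "associated with the use of Abraxane whether or not considered related to Abraxane", a drug that is not part of the study treatment. The SAP covers only the response-rate design and does not address AE capture.

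**The concern.** Sections 11.3 and 11.3.2 are not complementary rules for different events. Both cover AEs and SAEs, both start at consent, and both close early for withdrawal of consent or screen failure. They differ in length (4 weeks or 30 days) and, more importantly, in what starts the clock (drug alone, or the later of drug and ablation). No sentence ranks one above the other, so a site can follow either in good faith.

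The starting point matters only when an ablation falls on or after the last nivolumab dose, or the day before it. Section 4.2 leaves room for that:

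- The first ablation is placed within 7 days of the first dose and inside the 14-day first cycle. A patient who receives one dose and then the ablation, and no more drug, has an ablation after the last dose.
- Repeat ablations are allowed at least 60 days apart and are not tied to dosing. One performed while nivolumab is withheld follows the last dose if the hold becomes permanent.

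The calendar does not close the gap. Its toxicity-assessment row has no entry in the ablation column, so a late ablation has no toxicity visit of its own.

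At stake is the safety record. Under Section 16.0 the DSMB uses cumulative toxicity summaries to judge whether the trial should continue, change or stop. Those summaries could be built from windows of different length and starting point.

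**Working it through.** The plan states no figure to reproduce; the check is day-counting.

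**Inputs**

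- Section 11.3: capture ends 4 × 7 = 28 days after the last drug dose.
- Expedited Reporting: capture ends 30 days after the later of the last nivolumab dose and the last ablation.
- Footnote H: one evaluation at day 30, with 1 week allowed, so days 30 to 37 after the last drug dose.
- L = days from the last nivolumab dose to the last ablation. The documents give no distribution for L, so every value below is an assumption.

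**Formulas, with day 0 = last nivolumab dose**

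- End under Section 11.3: day 28.
- End under Expedited Reporting: day 30 + max(0, L).
- Of the 30 days after ablation, Section 11.3 covers 28 − L, limited to between 0 and 30. Days lost for L ≥ 0 are therefore min(30, L + 2). The cap is needed because no more than 30 days can be lost.

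| L (assumed) | End, Section 11.3 | End, Expedited Reporting | Post-ablation days lost, of 30 |
|---|---|---|---|
| 0 | 28 | 30 | 2 |
| 7 | 28 | 37 | 9 |
| 14 | 28 | 44 | 16 |
| 20 | 28 | 50 | 22 |
| 28 | 28 | 58 | 30 |
| 30 | 28 | 60 | 30 (window closed 2 days before the ablation) |

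**When dosing continues.** If a dose follows the ablation by 2 days, Section 11.3 runs to 2 + 28 = 30 days after the procedure and nothing is lost. With a dose 7 days later it runs to 7 + 28 = 35 days. What remains for these patients is the difference in length, 30 − 28 = 2 days at the end of the drug window.

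**The scheduled visit.** At L = 7 the footnote H evaluation falls 30 − 7 = 23 to 37 − 7 = 30 days after ablation. At L = 20 it falls 30 − 20 = 10 to 37 − 20 = 17 days after ablation. The visit itself (days 30 to 37) also comes after the Section 11.3 cut-off on day 28.

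**Conflicts inside the Expedited Reporting text.** Its late-SAE threshold is 4 weeks, counted from study discontinuation, beside a window of 30 days from treatment. It also ends AE evaluation when a new treatment begins, yet elsewhere reports all AEs to 30 days without that exception.

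**The case against.** A reader might infer that ablation complications in general go uncaptured. The documents do not support that, for these reasons:

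- The first ablation sits inside cycle 1 and nivolumab continues every 2 weeks. For patients who stay on drug, the first ablation is fully covered under either rule.
- Deaths within 30 days of drug or ablation are reportable under both the Expedited Reporting text and Section 11.5. Late SAEs suspected to be ablation-related also remain reportable under the Expedited Reporting text.
- Section 11.0 says AEs are recorded for the duration of the trial whatever their relationship to treatment. Calendar footnotes G and L require the procedure report, imaging report and consult notes for each ablation.
- At L = 7 the patient is still seen at the footnote H evaluation, 23 to 30 days after the procedure.
- Section 11.3.2 sits within Section 11.3 and reports go to one central office, so a clean split between sites following one rule and sites following the other is speculative.

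Most of this stands, and it narrows the point. It does not remove it. The recording statement in Section 11.0 adds another end point without resolving the conflict. Procedure reports and consult notes are not AE capture over a set period. Footnote H weakens the protection for late SAEs because it names only the drug. Placing one rule inside the section that states the other does not tell a site which to apply.

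The wrong drug name in Section 11.0 is leftover text and adds little weight, since Section 11.1 gives a product-neutral definition. The shorter related-death sentence does not cancel the fuller ones in Sections 11.3.2 and 11.5; it only fails to match them.

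**Conclusion.** The inconsistency holds, with limited reach. The loss of post-ablation days arises only for a patient whose last ablation has no nivolumab dose 2 or more days after it, and only where Section 11.3 is applied as written. It then ranges from a few days to the whole 30-day period, depending on the lag. How many patients this affects cannot be estimated from the documents.

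The events at risk are mainly non-serious ones and SAEs that the investigator does not attribute to ablation. The primary test and its operating characteristics are untouched, and safety is not among the listed objectives. The consequence is less complete and less uniform toxicity data on the combination for the DSMB. That justifies correcting the wording but does not call the design into question.

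**What to change.** Adopt one window throughout, using the one the sponsor has already written under Expedited Reporting: 30 days after the last nivolumab dose or ablation, whichever is later.

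1. Bring Section 11.3, the calendar column heading, footnote H and Section 13.0 into line with that window. In footnote H, extend the late-SAE sentence to ablation.
2. Within the Expedited Reporting text, align the 4-week late-SAE threshold with the 30-day window. Reconcile the sentence that ends AE evaluation at the start of a new treatment with the rule that all AEs are reported to 30 days, and check footnote H's version of it. Add *or ablation* to the related-death sentence so that it matches Sections 11.3.2 and 11.5.
3. In Section 11.3, extend the causality sentence to ablation.
4. As a clean-up, replace the wrong drug name in Section 11.0 with the study treatment, nivolumab or ablation.

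The cost is amendment wording and an occasional later AE contact after a late ablation. Sample size and analysis do not change.
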